5.1.1 Evaluating balance between the three treatment arms

Randomization is used to control for, or reduce, selection bias among study participants. Randomization should control for both measured and unmeasured confounders/covariates as well as both known and unknown confounders/covariates and background characteristics.

Comparison between groups will occur at the interim analysis at the end of the first influenza season and at the end of the study.

We will compare the three vaccination groups for basic background characteristics and known measured confounders (See Appendix *X*).

5.1.2 Relative Vaccine Effectiveness Estimate

Relative vaccine effectiveness (RVE) of cell-culture-based (FlucelvaxR) influenza vaccine as compared to egg-based influenza vaccines will be calculated using the following formula:

$$RVE_{cell} = \left(\frac{R_{egg} - R_{cell}}{R_{egg}}\right) X100\% = \left(1 - \frac{R_{cell}}{R_{egg}}\right) X100\%$$

Where:

 R_{cell} =incidence rate among the cell-culture-based influenza vaccination group R_{egg} =incidence rate among the egg-based influenza vaccination group

and

Relative vaccine effectiveness of recombinant HA (FluBlokR) influenza vaccines as compared to egg-based influenza vaccine will be calculated using the following formula:

$$RVE_{recombinant} = \left(\frac{R_{egg} - R_{recombinant}}{R_{egg}}\right) X100\% = \left(1 - \frac{R_{recombinant}}{R_{egg}}\right) X100\%$$

Where:

 $R_{recombinant}$ =incidence rate among the recombinant HA influenza vaccination group R_{egg} =incidence rate among the egg-based influenza vaccination group

The incidence rate equals the number of laboratory-confirmed influenza (definition 3.1.1) divided by the number of vaccinated individuals in each vaccination group.

The formula for the incidence rate will be:

 $Incidence Rate = \frac{Number of cases}{Number of vaccinated}$

Confidence intervals (95%) will be calculated using the standard formulas for relative risk. The upper and lower confidence intervals for relative vaccine effectiveness will be one minus the upper and lower calculated confidence intervals for the relative risk. The efficacy will be statistically significant if the calculated relative risk has a p-value of less than or equal to 0.025 (one-sided test). The interim analysis for relative effectiveness after the first influenza season uses a stricter p-value (<0.0001). Because of this, the final analysis will not need to adjust the p-value out of concerns about multiple looks.

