Subjects will be randomized in a 1:1:1 ratio to one of 3 vaccine formulations offered. Block randomization will be used in order to reduce bias and achieve balance in the allocation of subjects to treatment arms. An IDCRP biostatistician not involved in the study will generate a series of randomization vaccine codes. The roster for each site will be sent to the study staff, who, after enrolling the subject, will use the list to determine which vaccine each subject will receive. The vaccine allocations will be made sequentially using the roster.

9.6 Target Population:

Describe the population to whom the study findings will be generalized

U.S. military active duty members, midshipman, recruits, retirees, students, and their adult beneficiaries, along with U.S. adult population.

9.7 Benefit to the DoD:

State how this study will impact or be of benefit to the Department of Defense

If there are significant differences in either the immunogenicity or effectiveness between vaccines, influenza vaccination policy in the U.S. military may change to provide better protection against influenza. Conversely, if the differences in immunogenicity or vaccine effectiveness are minimal, the current immunization recommendations should not change. This study has the potential to provide high visibility to military infectious disease research, given the importance and global relevance of the research question being addressed

10.0

Study Procedures, Data Management, and Privacy

10.1 Study Procedures:

Describe step-by-step how the study will be conducted from beginning to end

Receipt of egg-based, cell-culture-based, or recombinant influenza vaccination is a requirement for study participation. All study assessments will be performed by members of the investigative team who are specifically designated to perform such activities in a clinical setting (according to site practices, local law, and as designated on the appropriate study documents). Study procedures will be performed in a clinical setting at participating MTFs (e.g., immunization clinic) or other clinical setting where vaccines are being administered in accordance with each site's vaccination policy.

Detailed Description of Assessments

Study Day/Follow-up Interval	Pre- Baselin Vax e	Post-Vax	Surveillanc e ILI	
	Day -30 Day 0 to 0	Day 21-35	Weekly ILI 28±7 (throughou sit t the flu 1 trigger season) date	
Eligibility assessment	Res earc Researc h			

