Influenza attack rates in the egg-based, cell-culture-based, and recombinant protein influenza vaccines arms of the study in the 2018-2019, 2019-2020, 2020-2021, and 2021-2022 seasons.

2. Ascertainment of primary outcome:

Laboratory-confirmed influenza as ascertained by a sensitive and specific assay is needed to assess effectiveness. The best assay is RT-PCR from nasopharyngeal swab specimens (various assay platforms); one particular antigen detection assay has similar sensitivity and performance characteristics, but numerous available rapid antigen detection tests for influenza are poorly sensitive and have poor negative predictive value, thus risking false-negative results if relied upon for outcome. There is heterogeneity across MHS clinical laboratories with respect to the type of test that is employed. A key factor is that individuals must present for care to have outcome ascertainment. Thus, follow-up methodology will involve strategies to increase likelihood of presentation for evaluation of incident ILI following vaccination.

3. Statistical analysis:

Incidence rates: To determine incidence, we will use the number of enrolled laboratoryconfirmed influenza cases by vaccine formulation as the numerator. For the denominator, we will use the number of enrolled subjects by vaccine formulation. We estimate that approximately 30- 40 percent of the subjects and will develop ILI symptoms. Of this group, perhaps 30 percent will seek care, with symptom severity the leading predictor for seeking care. We realize that there is no effective way in a large study to avoid the potential for bias in case ascertainment due to differences in symptom severity. As a pragmatic study, our goal is not to eliminate bias but to minimize the impact of bias , by using a broad but standardized case definition and by providing incentives for symptomatic individuals to be assessed. We can also use symptom severity data from the FLUPRO questionnaire to explore the extent to which symptom severity scores differs by region.

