Informed Consent Process - Enrollment

In response to a flyer or other print advertisement, a potential subject may call the study coordinator for more information regarding the study. The study coordinator will explain the study and/or ask the individual or group to come to the MTF for further discussion and possible enrollment. Following the recruitment procedures, those interested subjects will be offered the consent form and authorization forms to sign or paper or electronically. In accordance with DoD regulations, if a military member is interested in volunteering, their informed consent process will not take place in the presence of uniformed personnel in their chain of command or in the presence of a superior officer. At the time of consent, HIPAA authorization will also be obtained.

Study staff will be available to answer any questions an individual may have before deciding whether or not to participate in the study. When each individual has determined that they are interested in participating, they will sign the appropriate consent form in front of the designated study staff (listed in the Personnel and Collaborators Attachment). Each subject will have the ability to opt-in for a buccal swab and for same-day/post-vaccination self-collected blood samples. Subjects will elect to opt into this procedure in a designated area of the consent form and will do so without penalty or loss of entitlements. A copy of the signed ICD will be offered to the subject and the original document will be retained by the investigative team.

A subject is considered to be enrolled when they have signed a consent form and HIPAA authorization form (and California Bill of Rights, if applicable).

Substudy enrollment:

Study staff listed in the Personnel and Collaborators Attachment will ensure that each potential enrollee of the substudy is presented with the Substudy ICD. This ICD will be explained by the consenting study staff member and the potential participant will be able to ask any questions they may have. If a subject chooses to participate, the substudy ICD will be signed after the main ICD is completed and before any substudy procedures are done. Substudy participants will be offered a copy of their signed substudy ICD.

Participation Log

If individuals agree to participate, identifiers and the study ID, will be recorded in the participation log on a secure computer. Completed study procedures will be documented in the electronic participation log.

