3.0 Methods

3.1 Main trial

This study will be a multi-center, pragmatic, prospective, non-blinded randomized controlled trial to assess the relative effectiveness of the licensed egg-based inactivated influenza vaccine to two other licensed vaccines, the cell-culture-based inactivated influenza vaccine and the recombinant influenza vaccine, in the prevention of laboratory-confirmed influenza infection in active duty members, military retirees and beneficiaries over four consecutive influenza seasons. Subject recruitment will take place at military treatment facilities.

Subjects will be active duty service members or other adults at least 18 years of age who are DEERS-eligible for care in the military treatment facility.

A total of 18,000 eligible subjects will be randomly allocated in a 1:1:1 ratio by study investigative team staff to one of the following groups:

- Group 1: Cell-culture-based (FlucelvaxR) influenza vaccine (~6,000 subjects)
- Group 2: Recombinant HA (FluBlokR) influenza vaccine (~6,000 subjects)
- Group 3: Egg-based influenza vaccines (~6,000 subjects)

Vaccine type will be known to the study investigative team and the participant.

Study Period

All participants who are not Marine Corps recruits will undergo surveillance for ILI during the influenza season (from October 2018-May 2019, September 2019-May 2020, September 2020-May 2021, and September 2021-May 2022).

Process

[figure not shown]

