5.1.5 Plan for handling missing data and extreme values

Data will come from multiple sources including an enrollment document and from medical records. Care will be taken to minimize missing data, but sometimes this will still occur. For each variable, the data managers will review the data and calculate the percent missing. In addition, extreme values will be

identified. Participants with missing vaccination or outcome data will be excluded. A sensitivity analysis will be performed using only those non-recruit participants with at least 50%/75% of the weekly survey data in order to ensure that findings are consistent.

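### The protocol and SAP give different denominators for the primary attack rate, and neither specifies all randomised subjects by allocated vaccine

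*SAP*

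**What the plan says.** **Denominators.** SAP 5.1.2 takes the number of cases "divided by the number of vaccinated individuals in each vaccination group", and its formula repeats the number vaccinated as the divisor. Protocol 11.1 (Specific Aim 1, statistical analysis) says: "For the denominator, we will use the number of enrolled subjects by vaccine formulation". Protocol 13.4 ties enrolment to consent: "A subject is considered to be enrolled when they have signed a consent form and HIPAA authorization form". Under Protocol 13.1, consent may precede randomisation by up to 30 days.

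**Exclusions.** SAP 5.1.5 states: "Participants with missing vaccination or outcome data will be excluded".

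**Allocation.** Protocol 9.5 sends each site a roster, which staff use in sequence after enrolling a subject to see which vaccine is due. The trial is open (SAP 3.1): "Vaccine type will be known to the study investigative team and the participant".

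**What is absent.** Neither document defines an intention-to-treat, as-randomised or per-protocol set. Neither says how to count someone who declines the allocated vaccine or receives another. The loss-to-follow-up definition in Protocol 13.6 covers only people who received their allocated vaccine.

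**The concern.** SAP 5.1.1 relies on randomisation to control measured and unmeasured confounders. That protection belongs to the groups as randomised. A denominator that depends on something that happens after allocation, such as being vaccinated, keeps the protection only if that event is unrelated to the arm or to influenza risk.

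In a blinded trial a vaccinated-only set is usually harmless. Here staff and participants know the vaccine type, and Protocol 9.5 says that routine vaccine choice follows preference or availability, which the trial replaces with allocation. A participant could therefore decline or change product because of the arm drawn, and those who do so may differ in risk.

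There is also a plain conflict between the documents. Two analysts, one following the protocol and one the SAP, could compute the primary estimate on different sets of people. Neither would find an instruction for a subject who received a product other than the one allocated.

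**Working it through.** **1. The plan's own sample size.** Inputs from Protocol 11.5: one-sided alpha 0.025, power 0.80, attack rates 2.3% (egg) and 1.54% (each other arm), 15% loss to follow-up, 6,000 per arm.

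n = [1.960 × √(2 × 0.0192 × 0.9808) + 0.842 × √(0.023 × 0.977 + 0.0154 × 0.9846)]² / (0.023 − 0.0154)² = 5,117 per arm (pooled variance, no continuity correction)

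5,117 / 0.85 = 6,020, against 6,000 stated. The figure reproduces, so the sample size is not at fault. With 6,000 × 0.85 = 5,100 evaluable per arm, power is 79.9%.

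**2. Which people each rule counts.**

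| Subject | Protocol 11.1 | SAP 5.1.2 |
|---|---|---|
| Randomised, received allocated vaccine | counted | counted |
| Randomised, not vaccinated | counted if formulation means the one allocated; otherwise unclear | dropped |
| Randomised, received another product | arm not stated | arm not stated |
| Consented, never randomised | no formulation, so in no arm | not in any arm if not vaccinated |

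The rules differ in the second row. The third row is undefined in both.

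**3. Illustration of dropping decliners.** The share declining (d) and their risk relative to average (k) are assumptions, because the documents give neither. Assume no true difference between vaccines and declining in one non-egg arm only:

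RR = (1 − d × k) / (1 − d)

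| d | k = 2 | k = 0.5 |
|---|---|---|
| 1% | 0.98 / 0.99 = 0.990 | 0.995 / 0.99 = 1.005 |
| 3% | 0.94 / 0.97 = 0.969 | 0.985 / 0.97 = 1.015 |
| 5% | 0.90 / 0.95 = 0.947 | 0.975 / 0.95 = 1.026 |

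In counts, for d = 5% and k = 2 at 2.3% risk and 6,000 per arm: 300 decliners at 4.6% remove 13.8 of 138 expected cases. That leaves 124.2 / 5,700 = 2.18%, and 2.18 / 2.30 = 0.95.

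If the egg arm has the same d and k and its decliners are also dropped, the factor cancels and RR = 1.00.

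**4. Scale against sampling error.** With 138 cases in 6,000 per arm, SE(log RR) = √[2 × (1/138 − 1/6,000)] = 0.119. At d = 3% and k = 2, ln(0.969) = −0.031, about a quarter of one SE. With 117 egg-arm cases in 5,100, one-sided p < 0.025 needs 89 or fewer cases in the comparator (RR 0.76).

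**5. Cost of analysing by allocation.** Suppose a share s of a non-egg arm receives egg vaccine and is kept in its allocated arm. Its rate becomes (1 − s) × 1.54% + s × 2.3%. With 5,100 evaluable per arm:

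| s (one-way) | RR | Power |
|---|---|---|
| 0% | 0.670 | 79.9% |
| 2% | 0.676 | 78.1% |
| 5% | 0.686 | 75.3% |
| 10% | 0.703 | 70.3% |

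**The case against.** The strongest reply is that the randomised and vaccinated sets may be almost the same people. Randomisation and vaccination share the Day 0 column of the schedule in Protocol 10.1, and the same section makes receipt of one of the vaccine types a condition of participation. Losses between consent and randomisation come before allocation and cannot depend on arm. SAP 3.1 says that the participant knows the vaccine type, but not that this is before the injection. All of this stands, and it is why the effect may be negligible. It does not supply the missing analysis set. Protocol 9.5 also has staff reading the roster to choose the vaccine, so staff know the allocation before it is given.

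Three stronger readings are tempting, and the documents do not support them:

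- A reader might infer that switchers are moved to the arm of the product received. No text says so. Protocol 9.5 uses formulation for what is randomised: "Subjects will be randomized in a 1:1:1 ratio to one of 3 vaccine formulations offered". SAP 5.1.1, under a heading on treatment arms, says: "We will compare the three vaccination groups for basic background characteristics and known measured confounders". SAP 3.1 defines the groups by random allocation. The allocated-arm reading is at least as natural.
- A reader might infer that people who consented but were never randomised inflate the protocol's denominators. They have no formulation and so fall in no arm's count.
- A reader might infer that the missing-vaccination exclusion in SAP 5.1.5 removes decliners. A recorded refusal is known non-receipt, not missing data. The vaccinated-only divisor in 5.1.2 is what removes them.

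**Conclusion.** The point holds in a limited form. The primary denominator differs between the protocol and the SAP, and neither document specifies all randomised subjects by allocated arm. The SAP rule removes anyone randomised but not vaccinated, after an open allocation. The arm of a subject given another product is undefined.

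The size cannot be computed from the documents. Under the assumptions in the working, with decliners at twice the average risk and in one non-egg arm only, the shift is about 1% to 5% in the risk ratio. The direction depends on decliners' risk, and the shift vanishes if declining is equal in both arms. A shift of that size would not produce a significant result by itself, but it would move an estimate whose design target is RR 0.67. This is an inexpensive correction that should be made, not a flaw that undermines the trial.

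**What to change.** **Change**

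- In SAP 5.1.2 and Protocol 11.1, use one primary set: all randomised subjects, grouped by the vaccine allocated on the site roster, whatever was received.
- In SAP 5.1.5, state that non-receipt, or receipt of another product, is not a reason for exclusion.
- Start case counting at the same point for everyone, for example relative to the randomisation date. Surveillance now starts from vaccination (4 weeks after in Protocol 9.5, 14 days after in SAP 3.2), so an unvaccinated subject has no start, and the two intervals need reconciling.
- State how missing outcomes in unvaccinated subjects are handled. Adding them to the denominator without outcome capture would count them as non-cases. The influenza test results in the MDR pull (Protocol 10.2) are one source, with a sensitivity analysis. They are only partial, because Protocol 11.1 notes that clinical laboratories use different tests.
- Report declines and switches by arm.
- Keep the vaccinated-only or as-received analysis as a sensitivity analysis.

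**Cost**

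Most of this is wording, plus the rule for missing outcomes. Switchers dilute the estimate slightly: power goes from about 79.9% to 78.1% at an assumed 2% one-way switching. Some outcome data will still be missing for unvaccinated subjects.

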The ability of the study to detect a difference in effect is proportionate to the incidence of the outcome. A total of 172 influenza cases were reported among the 10,771 subjects enrolled in first three years of the study (2018-2021). The influenza attack rate has ranged from 0% in third season (COVID-19 pandemic), to 2.5% in the second season, with an overall attack rate 1.6% The observed attack rates are lower than baseline attack rates of 5% and 3% that formed the basis of sample size calculations for the first three years of the study. Consequently, the power to detect significant differences in VE between vaccine arms has been too low to due to the low attack rates. For the fourth year of the study is to increase the enrollment target from 15,000 to 18,00 to enhance power to detect significant differences in VE between attack rates are lower.

Secondary Aims:

Specific Aim #2:

Determine whether cell-culture-based and egg-based influenza vaccines give comparable HI and PVN titers to egg- and cell-matched vaccine antigens. An outcome of this objective is the potential to determine whether cell-culture-based vaccine antigens can provide broader coverage of circulating viruses than egg-based vaccine antigens.

Research Question: Is the proportion of subjects who seroconvert in either the cell-culture based or recombinant vaccine arm of the study greater than in the egg-based vaccine arm of the study.

There are two hypotheses of interest for Specific Aim 2, based on the seroconversion rates (SCR)

H₀: RR=1 vs H_A: RR < 1; p=0.025; The RR to be tested is defined as: 1) RR1=SCRcell / SCRegg and 2) RR2=SCRrecombinant / SCRegg

1. Endpoints:

- Humoral responses: HAI titer, anti-NA titer, virus-neutralizing titer
- Cellular responses (exploratory): frequency of antigen-specific CD4 and CD8 cells, B cells

SA 2.1: To obtain post-vaccination sera panels to determine breadth of reactivity to circulating strains.

This will be accomplished by recruiting consenting adults to an IRB-approved study conducted during a routine influenza vaccination campaign, collecting sera up to 30 days before and 21-35 days after vaccination with egg- or cell-culture-based or recombinant influenza vaccines. The samples will be de-identified and shipped to partner laboratories for aliquoting, storage, and antigenic analyses. We intend the study to be conducted during early vaccination campaigns performed at DoD facilities.

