11.5 Please provide a justification for your sample size

Main Study

Based on an alpha of 0.025 (1-sided) and a power of 0.80, a sample size of 18,000 (6,000 per arm) subjects has the power to detect a 33% difference in effectiveness between egg-based vaccine and two other vaccine preparations, assuming an influenza incidence of 2.3% in the egg-based arm and 1.54% in the cell-culture-based and recombinant arms. It assumes that 15% of subjects will be lost to follow-up.

Substudy

Based on an alpha of 0.025 (1-sided) and a power of 0.80, a sample size of 1,200 subjects (400/arm) has the power to detect a 22% relative difference in seroconversion rate if there is a 50% seroconversion at day 28 among the egg-based vaccine recipients. It assumes that 15-20% of subjects will be lost to follow-up.

11.6 Data Analysis Plan:

See section 11.1

12.0

Participant Information

12.1 Subject Population:

The study is comprised of DEERS-eligible adults (active duty, retirees and beneficiaries) vaccinated (at an MTF) (will be vaccinated) with one of the licensed egg-based, cell-culture-based or recombinant influenza vaccines during the 2018-2019, 2019-2020, 2020-2021, 2021-2022 influenza seasons in the United States. Subjects enrolled in the study during 2018-2019, 2019-2020, and/or 2020-2021 may also be enrolled in the 2021-2022 season.

12.2 Age Range:

Check all the boxes that apply. if the age range of potential subjects (specimens, records) does not match the range(s) selected, please specify in the text box.

0-17

- ✓ 18-24
- 25-34
- 35-44
- 45-54
- 55-64
- 65-74
- 75+

12.3 Gender:

- Male
- ✓ Female
- C Other

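### The primary relative risk takes no account of site or season; a stratified estimate would protect it if arm shares turn out uneven

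*SAP*

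**What the plan says.** - **Estimator.** SAP 5.1 covers the full study. In 5.1.2 each arm has one incidence: laboratory-confirmed cases "divided by the number of vaccinated individuals in each vaccination group". Relative vaccine effectiveness is one minus the ratio of two such proportions. On the interval the SAP says only: "Confidence intervals (95%) will be calculated using the standard formulas for relative risk". Success is a one-sided p-value of 0.025 or less. Protocol 11.1 uses the same numerator and denominator by formulation. The SAP never says that seasons and sites are pooled, but that is the plain reading of one numerator and one denominator per arm.
- **Site and season in the analysis.** Neither document gives the primary analysis a term, stratum or sensitivity analysis for either factor. SAP 5.1.1 relies on randomisation and a baseline comparison. In Appendix X, site is listed with a question mark and season is absent. Neither factor is in the subgroup list of SAP 4.2.
- **Randomisation.** Protocol 9.5 randomises within site, in blocks, at 1:1:1: "The roster for each site will be sent to the study staff". It does not say that rosters restart each season.
- **Risk by season.** Protocol 11.1: "The influenza attack rate has ranged from 0% in third season (COVID-19 pandemic), to 2.5% in the second season".
- **Exclusions.** SAP 5.1.5 leaves out participants whose vaccination or outcome data are missing.

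**The concern.** Site defines the allocation lists, and season strongly determines baseline risk. An analysis would normally respect the first and adjust for a prognostic factor as strong as the second. A crude ratio is safe only if the arms hold the same proportions of each season and site among the people analysed. Participants from a season with no influenza carry no information on the RR, yet they sit in the crude denominators. If one arm holds more of them, its attack rate falls for reasons unrelated to the vaccine. Uneven supply, or exclusions under SAP 5.1.5, could produce such a difference. At stake is the headline estimate and its one-sided p-value. In an open-label trial there is also the matter of choosing between crude and adjusted results after the data are in.

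**Working it through.** **1. The plan's own figure.** Protocol 11.5 gives 18,000 subjects (6,000 per arm), one-sided alpha 0.025 and power 0.80, "assuming an influenza incidence of 2.3% in the egg-based arm and 1.54% in the cell-culture-based and recombinant arms", with 15% loss. With the usual two-proportion formula and p̄ = 0.0192:

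n = [1.960·√(2·0.0192·0.9808) + 0.842·√(0.023·0.977 + 0.0154·0.9846)]² / 0.0076² ≈ 5,117 per arm.

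5,117/0.85 = 6,020, against 6,000 stated. The sample size reproduces.

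**2. How large the zero-event season can be.** Protocol 11.1 gives 172 cases in 10,771 subjects over three seasons (1.6%). Taking 2.5% as exact and as the maximum, seasons 1 and 2 together hold at least 172/0.025 = 6,880 subjects. Season 3 holds at most 10,771 − 6,880 = 3,891. Actual enrolment by season is not in the documents.

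**3. Equal shares in every stratum.** Let stratum k have n_k per arm, egg-arm risk p_k and a common RR.

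- Crude: Σ n_k·p_k·RR / Σ n_k·p_k = RR. Season 3 cancels.
- Mantel-Haenszel: Σ(a_k·n_ck/T_k) / Σ(c_k·n_ak/T_k) = RR. Here a and c are cases in the new-vaccine and egg arms, n_a and n_c their sizes, and T the total of the pair. Season 3 contributes zero to both sums.

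Two assumed enrolment patterns fit the reported totals: 3,000/4,000/3,771 and 1,500/6,000/3,271 in seasons 1-3. Season 4 takes the remaining 7,229. With season-4 rates of 1% to 4%, the season-stratified standard error is 0.2-0.4% smaller than the crude one. At RR 0.67, 15% loss and a season-4 rate of 2.3%, power is 70.6% crude and 70.8% stratified. The comparison is what matters here; the level depends on the assumed season-4 rate.

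**4. Unequal shares in season 3 only, true RR 1.** Let the egg share be s, with the other two arms splitting the rest. Expected cases are then equal in all arms, so the crude RR is the ratio of denominators:

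crude RR = [(18,000 − n₃)/3 + s·n₃] / [(18,000 − n₃)/3 + (1 − s)·n₃/2]

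| n₃ (assumed) | s | Crude RR | Season-stratified RR |
|---|---|---|---|
| 3,000 | 0.36 | 6,080/5,960 = 1.020 | 1.00 |
| 3,000 | 0.40 | 6,200/5,900 = 1.051 | 1.00 |
| 3,891 | 0.36 | 6,104/5,948 = 1.026 | 1.00 |
| 3,891 | 0.40 | 6,259/5,870 = 1.066 | 1.00 |

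This direction works against the new vaccines. The opposite imbalance favours them.

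**5. Effect on the one-sided test, true RR 1, egg arm at one third, season-4 rate 2.3%.** The rejection probability is Φ(−1.96 − ln(crude RR)/SE), with SE² = 1/a − 1/n_a + 1/c − 1/n_c. Ranges cover the two enrolment patterns in step 3.

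- New-vaccine arm at 40% of season 3: crude RR 0.960-0.965, type I error 0.046-0.050.
- The same arm also at 30% of season 2: crude RR 0.952-0.953, type I error 0.055-0.056.
- New-vaccine arm at 25% of season 3: crude RR 1.048-1.055, type I error 0.009-0.010.

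The season-stratified RR is 1.00 in each. The same reasoning applies to sites, but the documents give no site-level rates or counts to put in.

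**6. What stratifying cannot repair.** Suppose a new vaccine is missing for 20% of a season and the people enrolled in that window have 30% lower risk (both assumed). The new arm then holds 0.8/3 = 0.267 of the season, and the egg arm 0.267 + 0.1 = 0.367. The egg risk, relative to the rest of the season, is (0.267 + 0.1·0.7)/0.367 = 0.918. The RR within that season is 1/0.918 = 1.09 with no true effect, and season strata leave it there.

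**The case against.** Under the design as written, nothing is wrong with the crude estimate, and step 3 confirms it. The figures in steps 4 and 5 need imbalance that no part of the documents reports. An egg share of 36-40% in season 3 is an excess of 80-200 people at n₃ = 3,000, or 104-259 at 3,891. That is 3.1-8.8 standard deviations even under simple unblocked randomisation, so chance would not produce it. Supply gaps within the trial are not described: Protocol 9.5 mentions availability only in contrast to ordinary practice, and the egg arm may use any of three products. Following the randomisation supports strata by site only; adding season is covariate adjustment. SAP 5.1.1 also plans a balance check at the end of the study. All of this stands, and it limits the point to a safeguard. It does not make the crude ratio the better choice, because stratifying loses nothing when shares are equal.

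A reader might infer three stronger points that the material does not support:

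- **A power or sample-size error.** Steps 1 and 3 rule this out.
- **Bias from incomplete blocks.** In simulations with 5-15 sites and blocks of 6-12 (assumed), the 95% range of the crude RR under the null was at widest 0.998-1.002.
- **Invalid inference from repeat enrolment.** Protocol 12.1 says that earlier participants "may also be enrolled in the 2021-2022 season". With 30% repeats and a gamma frailty variance of 2 (assumed), the simulated variance of the test statistic was 0.96 if people were re-randomised and 1.04 if they kept their arm. The effect is minor.

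**Conclusion.** The gap is real and modest. The SAP's primary analysis leaves out both the site lists used for allocation and a season effect that ranges from no influenza to 2.5%. If 1:1:1 holds within each site and season, the consequence is nil for bias and type I error and under 0.5% for the standard error. If analysed shares differ between seasons, a crude RR 2-7% away from the truth is possible under the assumed shares in step 4. Under the shares in step 5, one-sided type I error runs from about 0.01 to 0.056. Those sizes rest on assumed season enrolments, an assumed season-4 rate and assumed arm shares. The documents do not show that such imbalance occurred, and they do not support saying that the planned estimate is biased. Stratifying protects against differences between strata. It does not correct shortages within a season or exclusions related to outcome.

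**What to change.** In SAP 5.1.2:

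- Make the primary estimate for each pairwise comparison a Mantel-Haenszel RR stratified by site and season.
- Take the 95% interval and the one-sided p-value from that same stratified analysis.
- State that strata with no events drop out, and fix in advance a rule for combining very small sites.
- Keep the crude RR as a supportive analysis.

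If a modified Poisson model with site and season terms is preferred, name it as an alternative. It is not equivalent to Mantel-Haenszel over site-by-season strata. It also has no finite coefficient for a season without events, so the SAP must say how that season is handled.

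The cost is SAP wording and a few lines of code. No extra subjects or new data are needed, since site and season of enrolment are already known. Protocol 11.1 describes its statistical plans as still open to change, so there is room for the amendment.
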